- I will ensure that any staff at my site(s) who are involved in the study conduct are adequately trained regarding this trial's operations, the protocol and their responsibilities. In the case of delegating any of my study responsibilities I will provide the sponsor with a delegation of investigators responsibilities log.
- I understand that the study may be terminated or enrollment may be suspended at any time by ViroMed, Inc. with or without cause, or by me or my institution if it becomes necessary to protect the best interest of the study patients.

Principal Investigator's Name (print)
mi d
Title
Address
Signature / Date

STUDY SYNOPSIS

PROTOCOL TITLE A Phase I/II, Open Label, Dose-Escalation Study to Assess the

Safety and Tolerability of VM202 in Patients with Painful Diabetic

Peripheral Neuropathy

STUDY PHASE I/II

INVESTIGATIONAL AGENT VM202

Dose Three doses will be tested: 4 mg, 8 mg and 16 mg VM202.

POPULATION Patients aged ≥ 18 years to ≤ 75 years diagnosed with painful

diabetic neuropathy in both lower extremities.

STUDY DESIGN A phase I/II, open label, dose-escalation, multicenter, 12-month

study designed to assess the safety and tolerability of unilateral intramuscular injection in the calf of VM202 in patients with painful diabetic peripheral neuropathy (DPN). The study will consist of three (3) cohorts with a total of 4 patients enrolled in

each cohort.

A Data Safety Monitoring Board (DSMB) will monitor patient safety throughout the study. After the first patient in a dose cohort completes the Day 30 follow-up evaluation and the other three patients enrolled in the same cohort complete at least the Day 14 follow-up (second dosing), an interim safety evaluation will be performed by the DSMB. If the DSMB recommends proceeding, the next dose cohort will be treated. This process will be repeated between the second and third dose cohort. All three dose cohorts will be followed for one year from the time of the first dose of study drug administration. If a dose limiting toxicity (DLT) is observed in one patient in any dose group, two additional patients will be added to the dose cohort in which the toxicity was observed. If no additional DLTs are observed in the 6 patients at

observed. If no additional DLTs are observed in the 6 patients at this dose level, it will be considered the Maximum Tolerated Dose (MTD). If a DLT occurs in 2 patients at any dose level, then the preceding dose level will be considered the MTD. The study will be stopped in the event that 2 DLTs occur at any point in the study.

NUMBER OF PATIENTS 12 to a maximum of 14

INCLUSION CRITERIA

- 1. Age \geq 18 years to \leq 75 years;
- 2. Documented history of Type I or II diabetes with current treatment control (glycosylated hemoglobin A_{1c} of $\leq 10.0\%$);
- 3. Diagnosis of painful diabetic peripheral neuropathy in both lower extremities;
- 4. The physical examination component of the Michigan Neuropathy Screening Instrument Score (MNSI) is ≥ 3 at Screening;
- 5. Visual analog scale (VAS) score of ≥ 4 cm at Screening (0 cm = no pain 10 cm worst imaginable pain);
- 6. Stable treatment of diabetes for at least 3 months with no anticipated changes in medication regimen, and no new symptoms associated with diabetes;
- 7. Lower extremity pain for at least 6 months; and
- 8. If female of childbearing potential, negative pregnancy test at screening and using acceptable method of birth control during the study.

EXCLUSION CRITERIA

- 1. Peripheral neuropathy caused by condition other than diabetes;
- 2. Other pain more severe than neuropathic pain;
- 3. Progressive or degenerative neurological disorder;
- 4. Myopathy;
- 5. Inflammatory disorder of the blood vessels (inflammatory angiopathy, such as Buerger's disease);
- 6. Active infection:
- 7. Chronic inflammatory disease (e.g. Crohn's, Rheumatoid Arthritis)
- 8. Positive HIV or HTLV at Screening
- 9. Positive Hepatitis B or C as determined by Hepatitis B core antibody (HBcAB), antibody to Hepatitis B antigen (IgG and IgM; HbsAB), Hepatitis B surface antigen (HBsAg) and Hepatitis C antibodies (Anti-HCV), at Screening or known immunosuppression or on chronic treatment with immunosuppressive drugs, chemotherapy or radiation therapy;
- 10. Stroke or myocardial infarction within last 6 months;
- 11. Ophthalmologic conditions pertinent to proliferative retinopathy or conditions that preclude standard ophthalmologic examination:
 - Cataract surgery within 6 months of trial;
 - Vascular lesions of the anterior segment of the eye (infection or ulceration of the cornea, rubeotic glaucoma, etc);
 - Vascular lesions of the posterior segment of the eye or proliferative retinopathy, macular edema, s/p

- photocoagulation for macular edema or proliferative retinopathy; sickle cell retinopathy, ischemic retinopathy due to retinal venous stasis or carotid artery disease;
- Choroidal angiogenesis; and
- Large elevated choroidal nevi, choroidal vascular tumors (choroidal hemangioma), or melanomas.
- 12. Specific laboratory values at Screening including: Hemoglobin < 9.0 g/dL, WBC < 3,000 cells per microliter, platelet count <75,000/mm³, Creatinine > 2.0 mg/dL; GFR < 50, AST and/or ALT > 2 times the upper limit of normal or any other clinically significant lab abnormality which in the opinion of the investigator should be exclusionary;
- 13. Use of gamma-linolenic acid (GLA), alpha lipoic acid or any other high dose dietary antioxidant supplement for symptomatic relief of DPN;
- 14. Uncontrolled hypertension as defined as sustained systolic blood pressure (SBP) > 200 mmHg or diastolic BP (DBP) > 110 mmHg at baseline/screening evaluation;
- 15. Patients with a recent history (<5 years) of or new screening finding of malignant neoplasm except basal cell carcinoma or squamous cell carcinoma of the skin (if excised and no evidence of recurrence);
- 16. Malignant tumors or abnormal screening test suspicious for cancer, or patients in whom screening exams indicate possible occult malignancy unless malignancy has been ruled out. Patients with family history of colon cancer in any first degree relative are excluded unless they have undergone a colonoscopy in the last 12 months with negative findings;
- 17. Elevated PSA unless prostate cancer has been excluded;
- 18. Subjects requiring > 81 mg daily of acetylsalicylic acid; If > 81 mg are taken at screening, subjects may be enrolled if willing/able to switch to another medication;
- 19. Major psychiatric disorder in past 6 months;
- 20. History of drug or alcohol abuse / dependence in the past 2 years;
- 21. History of recent tobacco abuse (within past 5 years);
- 22. BMI $> 45 \text{ kg/m}^2$;
- 23. Use of an investigational drug or treatment in past 12 months; and
- 24. Unable or unwilling to give informed consent.

STUDY PROCEDURES

Patients will be screened for study eligibility after giving informed consent. Screening should occur within the 60 days prior to Day 0 (day of injection). Screening will include assessment of study eligibility, a complete medical history, vital signs, physical exam,

photograph and measurement of ulcers (if any), cancer screening tests, viral screening, MNSI, VAS, 12 lead EKG, retinal fundoscopy, clinical chemistry, hematology, urinalysis, and pregnancy test (women of childbearing potential only), and documentation of any ulcers or gangrenous areas.

Patients will be treated with 4 mg, 8 mg or 16 mg of VM202 by intramuscular injections in the right calf on Day 0 and again on Day 14. VM202 will be delivered in a solution of 0.5 mg VM202 / mL in 0.5 mL injections. Patients in Cohort I will receive a final dose of 4 mg of VM202; Cohort II will receive a final dose of 8 mg VM202; and Cohort III will receive a final dose of 16 mg VM202.

Соновт	FINAL DOSE VM202	Number of Injections Day 0 Day 14		TOTAL VOLUME INJECTED
I	4 mg	8	8	8 mL
II	8 mg	16	16	16 mL
III	16 mg	32	32	32 mL

HGF serum levels will be determined immediately pre-treatment on Day 0, immediately pre-treatment on Day 14, on Day 30, and Day 60.

The number of copies of VM202 in whole blood will be determined at Day 0 (pre-injection, and 2 hours post injection), at Day 14 (pre-injection, and 2 hours post injection), Day 21, Day 30, Day 60 and Day 90.

VAS score, the SF-MPQ and BPI-DPN will be recorded at Day 30, Day 60, Day 90, at 6 months and 12 months. Retinal fundoscopy will be conducted at 12 months. Adverse events will be recorded throughout the one year follow-up period.

SCHEDULE OF EXAMINATIONS

Screening (Day -60 to Day 0)

Day 0

Day 14 ± 1 days

Day 21 ± 3 days

Day 30 ± 3 days

Day 60 ± 7 days

Day 90 ± 7 days

Month 6 ± 1 month

Month 12 ± 1 month

STUDY ENDPOINTS

The primary study endpoint is to evaluate safety and tolerability of intramuscular injection in the calf of VM202 in patients with painful DPN. Secondary endpoints include the assessment of the potential of VM202 to reduce the pain associated with DPN.

SAFETY

Any patient who receives VM202 will be included in the safety analysis population. Adverse events (including serious adverse events, and adverse events leading to treatment discontinuation) throughout the 12 month follow-up will be described according to severity and to their relationship with the study drug and / or device and procedure. Descriptive statistics (N, mean, median, SD, minimum and maximum values, where applicable) will be used to characterize safety parameters.

All patients will all undergo testing as presented in the American Cancer Society Cancer Screening Guidelines as part of their baseline testing to rule out cancer.

PHARMACOKINETICS

Determination of HGF serum levels will be determined immediately pre-treatment on Day 0, immediately pre-treatment on Day 14, Day 30, and Day 60. The number of copies of VM202 in whole blood will be determined at Day 0 (pre-injection, and 2 hours post injection), at Day 14 (pre-injection, and 2 hours post injection), Day 21, Day 30, Day 60 and Day 90.

EFFICACY

This is a phase I /II study, not powered to assess efficacy. However, descriptive statistics (N, mean, median, SD, minimum and maximum values, where applicable) of clinically meaningful endpoints will be tabulated. Change in pain level, as measured by the VAS, SF-MPQ and BPI-DPN will be recorded. The status of preexisting ulcers will also be reported.

TABLE OF CONTENTS

Inv	ESTIGATO	DR'S AGREEMENT	2
STU	DY S YNC	PSIS	3
Тав	LE OF CO	ONTENTS	8
GLO	SSARY		12
		AND FACILITIES	
1.		ROUND	
	1.1.	Diabetes	
	1.2.	Current Treatment Options	
	1.2.	-	17
			17
		1.2.3. Other Treatment Options	18
			18
	1.3.	HGF for the Treatment of Diabetic Neuro	
	1.4.	VM202	
	1.5.	Preclinical Data	
	1.6. 1.7.	Clinical Data Study and Dose Rationale	
2		·	
2.		CLINICAL PRACTICES STATEMENT	
3.		IGATIONAL PLAN	
	3.1.	Study Objectives	
	3.2.	Study Design	
	3.3.	Patient Population	
	3.4.	Study Procedures	
	5.1.	· · · · · · · · · · · · · · · · · · ·	

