3.2. STUDY DESIGN

This is a phase I/II, open label, dose-escalation, multicenter, 12 month study. Patients with painful DPN will be screened for study eligibility after giving informed consent. Patients will be treated with 4 mg, 8 mg or 16 mg of VM202 by intramuscular injections in the right calf on Day 0 and again on Day 14. Study drug will only be administered unilaterally. If injection in the right leg is medically contraindicated, the left leg may be treated and noted on the appropriate case report form.

VM202 will be delivered in a solution of 0.5 mg VM202 / mL. Individual injections will be 0.5 mL. Patients in Cohort I will receive 2 mg of VM202 on Day 0 and Day 14 for a final dose of 4 mg; Cohort II will receive 4 mg of VM202 on Day 0 and Day 14 for a final dose of 8 mg; and Cohort III will receive 8 mg of VM202 on Day 0 and Day 14 for a final dose of 16 mg VM202. Table 2 lists the final dose and number of injections to be administered by study cohort. Patients will be followed for a period of 12 months.

Table 2. VM202 administration for each cohort

Сонокт	FINAL DOSE VM202	Number of Injections Day 0 Day 14		TOTAL VOLUME INJECTED
I	4 mg	8	8	8 mL
II	8 mg	16	16	16 mL
III	16 mg	32	32	32 mL

This is a dose escalation study. Cohorts of increasing dose will be enrolled sequentially. Dose escalation decisions (permission to treat at higher doses) will be made by the Data Safety Monitoring Board (DSMB) based on review of adverse events and on the occurrence of dose limiting toxicities (DLT) in each cohort. The decision to proceed to the next higher dose cohort will be made according to the following scheme.

After the first patient in a dose cohort completes the Day 30 follow-up evaluation and the other three patients enrolled in the same cohort complete at least the Day 14 follow-up (second dosing), an interim safety evaluation will be performed by the DSMB.

- If no DLT is observed at the current dose cohort, then the dose may be escalated as planned for the next cohort.
- If a DLT is observed in one patient in a dose group, then 2 additional patients will be treated at the same dose level. If no further DLTs are observed in the additional patients at Day 30, then that Dose will be considered the Maximum Tolerated Dose (MTD).
- If a DLT occurs in 2 patients, then the preceding dose level will be considered the MTD.

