If a DLT is observed in a patient in a dose cohort with complete enrollment, but after a dose escalation has occurred, further dose escalation may be delayed pending review of the data. If 2 patients in a dose cohort experience a DLT, then the study will be stopped.

A DLT is defined as any of the following SAEs:

- acute anaphylaxis (including erythema, hives, wheezing, stridor or respiratory distress) attributable to VM202 injection;
- temperature >102°F with negative blood cultures and in absence of viral syndrome within 24 hours of study drug administration; or
- evidence of active tissue necrosis of grade 3 or greater at the injection site within two weeks of study drug administration.

The DSMB will make a formal recommendation to proceed (or not proceed) to the next dose cohort between the first and second dose cohort, and again between the

second and third dose cohort (if applicable). The DSMB will monitor patient safety throughout the 12 month follow-up period.

[figure not shown]

Figure 3. Study flowchart

Screening/Baseline assessments should occur within the 60 days prior to Day 0 (day of injection). Baseline assessments include assessment of study eligibility, a complete medical history, vital signs, complete physical exam, photograph and measurement of ulcers (if any), cancer screening tests, viral screening, MNSI Score, VAS, 12 lead EKG, retinal fundoscopy, clinical chemistry, hematology, urinalysis, and pregnancy test (women of childbearing potential only), and documentation of any ulcers or gangrenous areas.

Patients will be treated with 8, 16 or 32 – 0.5 mL intramuscular injections in the right calf of VM202 on Day 0 and again on Day 14. Each injection will contain 0.25 mg VM202. The first cohort of patients will receive a total dose of 4 mg of study product in 8 mL of solution (eight injections on Day 0, and eight injections on Day 14). The second cohort of patients will receive a total dose of 8 mg of study product in 16 mL of solution (sixteen injections on Day 0, and sixteen injections on Day 14). The third cohort of patients will receive a total dose of 16 mg of study product in 32 mL of solution (thirty-two injections on Day 0, and thirty-two injections on Day 14).

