3.3. PATIENT POPULATION

Up to 14 evaluable patients with DPN meeting the following study entry criteria will be enrolled.

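### The only numeric stopping rule has two wordings: 2 DLTs anywhere in the study (synopsis) or 2 patients with a DLT in one cohort (Section 3.2)

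*Combined protocol and SAP*

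**What the plan says.** The Study Design part of the synopsis states: "The study will be stopped in the event that 2 DLTs occur at any point in the study". It sets no same-cohort condition and counts DLTs. Section 3.2 states: "If 2 patients in a dose cohort experience a DLT, then the study will be stopped". That rule is limited to one cohort and counts patients.

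Three related rules bear on this:

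- **Expansion.** Section 3.2: "If a DLT is observed in one patient in a dose group, then 2 additional patients will be treated at the same dose level". The synopsis agrees.
- **MTD.** Section 3.2: "If a DLT occurs in 2 patients, then the preceding dose level will be considered the MTD", with no dose-level limit. The synopsis ties the same conclusion to 2 patients at one dose level.
- **Late DLTs.** For a DLT in a fully enrolled cohort that appears after escalation, Section 3.2 permits a delay in further escalation but does not require one.

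The DSMB reviews a cohort once its first patient has completed Day 30 and the other three have completed at least the Day 14 second dosing. One of the three DLT definitions, necrosis of grade 3 or worse, runs for two weeks after dosing. Section 6 has no stopping rule, and Section 3.5.3 gives only the sponsor's general right to end the study. Figure 3, the flowchart, was not available to me.

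**The concern.** Safety is the primary endpoint, and Section 6 names the MTD as the primary goal. This is the one numeric rule that ends the trial, so the DSMB should not have to choose between two versions of it after a second DLT.

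Suppose a Cohort I DLT comes to light after Cohort II has opened, and a Cohort II patient then has one. The synopsis stops the study. Section 3.2 read alone does not: each cohort has one affected patient, and the expansion rule could add two patients at a dose that has just produced a DLT. Similarly, one patient with a DLT after each dose meets the synopsis rule but not the Section 3.2 rule.

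**Working it through.** **The plan's own figure.** The stated maximum is 14. Three cohorts of 4 plus one expansion of 2 gives 3 × 4 + 2 = 14, so it reproduces.

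**Nesting.** Two affected patients in one cohort are at least two DLTs in the study. Whenever the Section 3.2 rule fires, the synopsis rule has fired too. The reverse fails in two cases:

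- (a) one affected patient in each of two cohorts;
- (b) two DLTs in one patient.

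**Can (a) occur?** If every DLT is seen at review, a single DLT expands that cohort and escalation ends there, so a second affected patient falls in the same cohort and the rules agree. Case (a) therefore needs a DLT unseen at review. At the earliest permitted review, the necrosis window may still be open for the second doses of patients 2 to 4, which is 3 of the cohort's 4 × 2 = 8 patient-doses.

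**Inputs.** From the protocol: 3 cohorts, 4 patients each, 2 doses, and the review timing. Assumed, because the documents give neither: the per-patient DLT risk p (the same in all cohorts) and the share L of second-dose DLTs in patients 2 to 4 that are unseen at review. DLTs in expansion patients are not counted, and a late DLT is taken not to hold escalation.

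**Formula for (a).**

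- Per-dose risk: w = 1 − √(1 − p).
- Unseen DLT in one of patients 2 to 4: u = w(1 − w)L.
- Cohort passes review with exactly one late DLT: A = 3u(1 − p)³.
- Cohort is clean: B = (1 − p)⁴.
- Cohort has exactly one affected patient: C = 4p(1 − p)³.
- Probability of (a) = A(C − A) + A²(B + C) + 2ABC.

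The three terms are: late in I with a DLT seen in II; late in both I and II, with at most one in III; and late in I or II, with the other clean and one in III.

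At p = 4.94% and L = 0.25: w = 0.0250, u = 0.0061, A = 0.0157, B = 0.8166, C = 0.1698. The terms are 0.0024 + 0.0002 + 0.0044 = 0.0070.

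**Formula for (b), all DLTs seen.** One patient has a DLT after both doses, nobody else in that cohort is affected, and all earlier cohorts are clean: 4w²(1 − p)³ × (1 + B + B²). At p = 4.94% this is 0.00215 × 2.483 = 0.0053. It assumes re-dosing after a first DLT and independent windows.

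| p | w | (a) L = 0 | (a) L = 0.10 | (a) L = 0.25 | (b) |
|---|---|---|---|---|---|
| 1% | 0.5% | 0 | 0.02% | 0.04% | 0.03% |
| 2% | 1.0% | 0 | 0.06% | 0.15% | 0.11% |
| 4.94% | 2.5% | 0 | 0.28% | 0.70% | 0.53% |
| 9.75% | 5.0% | 0 | 0.70% | 1.74% | 1.55% |
| 19% | 10% | 0 | 1.08% | 2.67% | 3.43% |

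With L = 0.5, case (a) ranges from 0.08% to 5.3%. With risk rising by cohort and L = 0.25, it is 0.2% (1%, 2%, 4.94%) or 0.7% (2%, 5%, 10%).

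**The case against.** The strongest reply is that the sentences do not truly conflict. They are nested, so obeying both means stopping under the synopsis rule. That stands, and it rules out an inference a reader might draw, that the protocol leaves no safe course. What remains is that nothing tells the DSMB to apply both, and the full escalation scheme and the DLT definitions sit in Section 3.2.

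Second, other controls exist. Sections 3.4.3 and 3.4.4 make a site wait for enrolment confirmation and for the sponsor or its designee to authorise each patient's treatment, so no site can proceed alone. The DSMB monitors throughout. Authorisation also takes time, during which a necrosis window may close before the next cohort is dosed; the model has no such interval. Fever within 24 hours and acute anaphylaxis would mostly be seen around the Day 14 visit, and the Day 14 condition is a minimum. All of this pulls case (a) towards the low end.

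Third, the synopsis may use DLTs loosely for patients with a DLT. If so, case (b) disappears. The text does not say so, and investigators may well withhold a second dose after a DLT, although no rule requires it.

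Fourth, the cap may seem to settle the scope: "NUMBER OF PATIENTS 12 to a maximum of 14" in the synopsis and "Up to 14 evaluable patients with DPN meeting the following study entry criteria will be enrolled" in Section 3.3. It does not. Fourteen fits the study-wide rule, and it also fits Section 3.2 when every DLT is seen before escalation, because the one expanded dose is then the MTD. Conversely, a reader might infer that Section 3.2 would let enrolment reach 3 × 6 = 18. The documents do not support that, because it would breach the stated cap.

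**Conclusion.** The two sentences differ in scope and in unit, and no available text ranks them. For a safety decision rule this is wrong as written and should be repaired, but the practical exposure is small: case (a) in 0% to 2.7% of trials for up to 25% unseen, and case (b) in about 0.03% to 3.4%, over assumed flat risks of 1% to 19%. These sizes depend on the assumed risk and unseen share and, for (b), on re-dosing and independence.

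A reader might infer a much larger gap by treating all 12 patients as enrolled regardless of results. At 5% risk, the chance of 2 or more affected patients is 11.8% study-wide against 4.2% in some single cohort; at 10% it is 34.1% against 14.9%. The protocol does not support that comparison, because escalation does not proceed past a DLT seen at review, and with all DLTs seen the patient-count gap is zero.

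Figure 3 should be checked. Even if it is clear, the two sentences would still differ.

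**What to change.** Use one sentence in both the synopsis and Section 3.2, keeping the stricter scope and stating the unit. For example: *The study will be stopped if 2 DLTs occur in total, in the same or different patients and in the same or different dose cohorts.* If the sponsor prefers to count patients, the protocol should say so openly, since that loosens the synopsis rule for repeat DLTs, and should add that a patient with a DLT after the first dose does not receive the second.

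In Section 3.2, replace the optional delay after a late DLT with a hold on further escalation until the DSMB has reviewed it. Align the MTD sentences in the synopsis and Section 3.2 so that it is clear how the MTD is set when the two DLTs occur at different doses. Make Figure 3 match if it shows a stopping rule.

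The cost is wording only, with no added patients or data. The study would stop slightly more often than under Section 3.2 alone, by roughly the percentages above, and a hold could delay the next cohort.
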